8.5. Pharmacokinetics

Blood and feces for the determination of IW-3300 in plasma and stool, respectively, will be collected from all dosed subjects during the Clinic Period at timepoints specified in the SoA ([Table 1](#)). Instructions for the collection and handling of biological samples will be provided by the sponsor. The actual date and time (24-hour clock time) of each sample will be recorded.

The following PK parameters will be calculated using a noncompartmental approach:

- Area under the plasma concentration time curve from time zero to the time at which the last measurable concentration is observed (AUC_{0-t})
- Area under the plasma concentration time curve from time zero to time infinity ($AUC_{0-\infty}$)
- Maximum plasma concentration (C_{max})
- Time to maximum plasma concentration (T_{max})
- Terminal elimination half-life ($t_{1/2}$)

The wet weight of stool collected during the postdose collection period prior to Discharge will be measured and the total amount of IW-3300 in stool will be calculated, including concentration of IW-3300 in stool (ng/g), and percent recovery.

Genetic analyses will not be performed on these samples. Subject confidentiality will be maintained. At visits during which blood samples for the determination of multiple aspects of IW-3300 will be taken, 1 sample of sufficient volume can be used.

Drug concentration information that may unblind the study will not be reported to investigative sites or blinded personnel until the study has been unblinded.

8.6. Pharmacodynamics

Subjects will enter BM-related information into a paper diary, the BBMD, on an event-driven basis (ie, following each BM) in accordance with the instructions in the SoA ([Table 1](#)).

The BM-related information will include the day and time of BMs and a report of stool consistency for each BM using the BSFS (1=Separate hard lumps like nuts [difficult to pass] to 7=Watery, no solid pieces [entirely liquid]).

Subjects will enter bladder information into the BBMD, which will include the following questions:

In the past 24 hours...

- Did you have to urinate more frequently than normal? (yes/no)
- How many times did you urinate? (0 to 2; 3 to 6; 7 to 10; or 10+ times)
- Did you feel the strong need to urinate with little or no warning? (yes/no)
- Did you have to get up to urinate during the night more frequently than usual? (yes/no)
- How many times did you have to get up at night to urinate? (0, 1, 2, 3+ times)
- Did you have pain or burning in your bladder or pelvic area? (yes/no)

8.7. Genetics

Genetics are not evaluated in this study; no samples will be collected for genetics research.

8.8. Biomarkers

Biomarkers are not evaluated in this study; no samples will be collected for biomarker research.

8.9. Immunogenicity Assessments

Immunogenicity is not evaluated in this study; no samples will be collected to evaluate antibodies to IW-3300.

8.10. Medical Resource Utilization and Health Economics

Medical resource utilization and health economics parameters are not evaluated in this study.

9. STATISTICAL CONSIDERATIONS

9.1. Statistical Hypotheses

No hypothesis testing is planned.

9.2. Sample Size Determination

No statistical sample size determination process was performed. The sample size chosen for each cohort (8 subjects) is considered sufficient for evaluation of safety, tolerability, PK, and PD.

9.3. Populations for Analyses

The following populations are defined:

Population	Description
Screened Analysis Set	The Screened Analysis Set consists of all subjects who have signed informed consent.
ITT Set	The ITT Set consists of all subjects in the Screened Analysis Set who have been randomized to a treatment regimen. Analysis will be performed according to the allocated treatment regimen regardless of the treatment regimen actually received.
Safety Analysis Set	The Safety Analysis Set consists of all subjects who receive any amount of study drug. Analysis will be performed according to the treatment actually received regardless of the allocated treatment.
PK Analysis Set	The PK Analysis Set consists of all subjects in the Safety Analysis Set who have at least 1 postdose PK assessment. Analysis will be performed according to the treatment actually received regardless of the allocated treatment.
PD Analysis Set	The PD Analysis Set consists of all subjects in the Safety Analysis Set who have at least 1 postdose BBMD entry in the Clinic Period. Analysis will be performed according to the treatment actually received regardless of the allocated treatment.

9.4. Statistical Analyses

The statistical analysis plan (SAP) will be finalized prior to the clinical database lock and will include a more technical and detailed description of the statistical analyses described in this section.

9.4.1. General Considerations

For summaries by treatment group, data from subjects who receive placebo in different cohorts can be combined and presented as one treatment group (referred to as “treatment” and “placebo”), as appropriate.

Continuous variables will be summarized using descriptive statistics (N, mean, SD, median, minimum, and maximum). Categorical variables will be summarized using the count and

proportion of subjects in each category. Furthermore, PK data will be summarized using descriptive statistics, geometric mean, and coefficient of variation (CV%) of the geometric mean.

9.4.2. Primary Endpoints Analyses

The primary endpoint analysis will be based on the Safety Analysis Set.

AE verbatim terms will be coded in the electronic data capture (EDC) system against the most current version of the Medical Dictionary for Regulatory Activities (MedDRA) available at the start of the study.

TEAEs are defined in Section 10.3.1. The TEAEs and TESAEs for 1 calendar day postdose will be summarized by system organ class, preferred term, and treatment (or cohort).

9.4.3. Secondary Endpoint Analysis

Not applicable.

9.4.4. Exploratory Endpoints Analyses

PK analyses will be based on the PK Analysis Set.

Plasma concentrations of IW-3300 will be summarized by treatment (or cohort) at each assessment timepoint; additionally, a listing of plasma concentrations will be provided. PK parameters (as described in Section 8.5) will also be calculated for each subject and summarized by treatment, if systemic levels of IW-3300 are measurable/as data permit (≥ 1 plasma concentration above the lower limit of quantitation [LLOQ] is necessary for calculation of C_{max} and T_{max} ; ≥ 3 plasma concentrations above LLOQ are necessary for calculation of AUC_{0-t} , $AUC_{0-\infty}$, and $t_{1/2}$).

The total amount of IW-3300 in stool collected during the postdose collection period prior to Discharge will be summarized by treatment, including the concentration (ng/g; based on the wet weight of stool) and the percent recovery. Subjects who do not have a BM during the stool collection period will not be included in the analysis of IW-3300 in stool.

The analysis of the BBMD parameters will be based on the PD Analysis Set.

BBMD parameters (BM frequency, stool consistency, urinary frequency, urinary urgency, and nocturia) will be summarized by treatment (or cohort) for each study period (Screening Period and Clinic Period) using descriptive statistics and changes from baseline will be calculated whenever it is appropriate.

Baseline BM values will be derived from the BBMD data collected in the Screening Period, specifically, the period of time from 7 days prior to Check-in up to the time of randomization on Day 1. The baseline BM frequency rate (BMs per day) will be derived based on the number of BMs the subject reports during this period. The baseline stool consistency will be calculated as the average of the nonmissing BSFS scores associated with the BMs reported by the subject during this period.

The subjects reported assessments for urination category parameters (urinary frequency, urinary urgency, and nocturia) in the 24-hour period prior to drug administration on Day 1 will be used to establish the baseline for each urinary parameter. The subjects reported assessment of pain or

burning in the bladder or pelvic area in the 24-hour period prior to drug administration on Day 1 will be used to establish the baseline for this parameter.

The Clinic Period values will be derived from the BBMD data collected after randomization in the Clinic Period, specifically, the period of time from Day 1 (postrandomization) through Day 2 (Discharge). The Clinic Period BM frequency rate will be derived based on the number of BMs the subject reports during this period. The Clinic Period stool consistency score is the mean of the nonmissing BSFS scores associated with the BMs reported by the subject during this period.

The subjects reported assessments for urination category parameters (urinary frequency, urinary urgency, and nocturia) in the 24-hour period after dosing on Day 1 will be used to establish the postbaseline assessments for each parameter. Subjects reported assessment of pain or burning in the bladder or pelvic area in the 24-hour period after dosing on Day 1 will be used to establish the postbaseline assessments for this parameter.

For the continuous variables, change from baseline will be defined as the Clinic Period value minus the baseline value. For the categorical variables, category shift from baseline to the Clinic Period will be assessed.

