1.1.7. Number of Subjects

A maximum of 40 subjects will be randomized in the study (up to 5 cohorts of 8 subjects each); within each cohort, 6 subjects will be randomized to IW-3300 and 2 subjects will be randomized to placebo.

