^f Procedure will be done in the morning shortly after the subject awakens but before the subject eats breakfast.

^g The BM portion of the BBMD will be completed by the subject on an event-driven basis. For subjects with Screening Visits earlier than Day -9, CRU staff will call subjects on Day -9 to remind them to begin recording their BMs in the BBMD the following day, answer any questions, and provide replacement BBMD pages via email, if needed. Bladder and urination information in the BBMD will be collected on Day 1 predose and Day 2, with a 24-hour recall period at each timepoint.

^h CRU staff will review the subject's Screening Period BBMD at Check-in to confirm that subjects have at least 3 bowel movements during the 7 days prior to Check-in (Days -8 through -2) and no more than 3 bowel movements per day to be eligible for the study; CRU staff will collect the subject's Clinic Period BBMD at Discharge.

ⁱ Subjects will remain at the CRU from Check-in (Day -1) through Discharge (Day 2).

j. Subjects will fast for at least 6 hours prior to dosing on Day 1 and for at least 1 hour following dosing.

k. Study drug (IW-3300 or placebo low-volume enema) will be administered rectally after a fast of at least 6 hours. Subjects will be encouraged to empty their bowels in the morning prior to dosing, if possible. Subjects will be instructed to lie on their left side with their left leg extended and their right leg slightly bent. CRU staff will remove the cap from the applicator tip and gently insert the tip into the subject's rectum, then slowly squeeze the bottle to empty the contents into the rectum. After using the enema, subjects will lie on their left side for at least 30 minutes to allow the liquid to distribute throughout their intestines, followed by at least 30 additional minutes in the semisupine position. CRU staff will monitor subjects for leakage of the study drug from the rectum during the initial 30 minutes post administration. Subjects should avoid using the bathroom and hold in the enema for at least 1 hour.

l. PK blood draws at 0.5 and 1 hour postdose should be collected while the subject maintains the position noted in the dosing instructions above.

m. Beginning immediately after dosing on Day 1, all stool passed up to the time of Discharge on Day 2 will be collected and the wet weight will be measured, to calculate IW-3300 concentrations in stool.

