3.3.2. Exploratory Endpoints (Pharmacokinetics and Pharmacodynamics)

The exploratory endpoints are:

- PK parameters
- Total amount of IW-3300 in stool (concentration and percent recovery)
- Change from baseline in BM frequency during the Clinic Period
- Change from baseline in stool consistency (BSFS score) during the Clinic Period
- Change from baseline in urinary frequency during the Clinic Period for a 24-hour duration
- Change from baseline in urinary urgency during the Clinic Period for a 24-hour duration
- Change from baseline in nocturia during the Clinic Period for a 24-hour duration
- Change from baseline in pain or burning in bladder or pelvic area during the Clinic Period for a 24-hour duration

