4.1.1.2. Clinic Period

The Clinic Period will begin at Check-in to the Phase 1 CRU on Day -1 (the day before dosing), and will end at the time of Discharge on Day 2 (the day after dosing). Following confirmation of eligibility at Check-in, subjects will be admitted to the CRU and will undergo baseline procedures. On the morning of Day 1 (note that there is no Day 0), subjects in each cohort will undergo predose assessments and will be randomized in a 3:1 ratio to receive IW-3300 or matching placebo after a fast of at least 6 hours. In Cohort 1 only, the first 2 subjects will be randomized in a 1:1 ratio to IW-3300 or placebo and dosed at least 4 hours before the remaining subjects in the cohort.

Blood and stool samples for PK assessments will be collected at specified times predose (blood) and postdose (blood and stool) during the Clinic Period (see SoA in [Table 1](#)). Throughout the Clinic Period, safety assessments will be performed and subjects will continue to enter their BM information into the BBMD on an event-driven basis. Bladder and urination information in the BBMD will be collected on Day 1 predose and Day 2, with a 24-hour recall period at each timepoint. Subjects will be confined to the CRU from Check-in (Day -1) through 1 day of dosing until Discharge (Day 2), which will occur after completion of the assessments (at least 24 hours after administration of study drug) and at the investigator's discretion.

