5.1.2. Type of Subject and Disease Characteristics

2. Subject is medically healthy with no clinically significant findings during medical evaluation including physical examination, 12-lead ECG, and clinical laboratory tests (serum chemistry, hematology, urinalysis, and urine drug and alcohol screen). (NOTE: In making this determination, the investigator or designee will consider whether any finding could prevent the subject from performing any of the protocol-specified assessments, could represent a condition that would exclude the subject from the study, could represent a safety concern if the subject participates in the study, or could confound the study-specified assessments).
3. Subject has normal formed bowel movements (≥ 3 per week and ≤ 3 per day; average BSFS score of >2 and <6 , as reported in the BBMD during the 7 days before Check-in [Day -1]).
4. Subject agrees to refrain from making any new or major lifestyle changes (eg, new diet or exercise regimen) from the Screening Visit until after the Follow-up Phone Call on Day 14.
5. If subject is ≥ 45 years of age, subject is compliant with colorectal cancer screening guidelines according to the ACG Clinical Guidelines: Colorectal Cancer Screening 2021. (9)

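### Stool recovery is summarized only in subjects who had a BM, although no BM before Discharge is an observed recovery of zero, not a missing value

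*Protocol*

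**What the plan says.** Stool recovery is an exploratory PK endpoint (Protocol 3.3.2). Under Protocol 8.5, "the total amount of IW-3300 in stool will be calculated, including concentration of IW-3300 in stool (ng/g), and percent recovery". The analysis is in Protocol 9.4.4: "The total amount of IW-3300 in stool collected during the postdose collection period prior to Discharge will be summarized by treatment", with concentration per wet weight and percent recovery as components. The next sentence is the restriction: "Subjects who do not have a BM during the stool collection period will not be included in the analysis of IW-3300 in stool". It makes no distinction between the three measures.

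Collection is exhaustive. The stool-collection footnote to the Schedule of Activities (Protocol 1.3) says that, from dosing on, "all stool passed up to the time of Discharge on Day 2 will be collected and the wet weight will be measured". Subjects are confined to the unit until Discharge, which takes place "at least 24 hours after administration of study drug" (Protocol 4.1.1.2). On numbers, Protocol 1.1.7 says that "within each cohort, 6 subjects will be randomized to IW-3300 and 2 subjects will be randomized to placebo".

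The SAP lists the same endpoint (3.2.2) but sends all PK analysis to a separate PK analysis plan (Section 8), which is not among the documents. Neither document enters a zero for a subject without a BM, plans a supportive summary, or asks for the number excluded at each dose.

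**The concern.** The quantity defined is the drug found in stool between dosing and Discharge. A confined subject whose stool is all collected, and who passes none, has a known value for it: 0 ng, or 0% of the dose. Leaving that subject out treats an observed zero as missing data. Exclusion is right only for ng/g, which has no denominator without stool.

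The rule also selects on a postdose event that the protocol itself studies as a possible drug effect. BM frequency is an endpoint (3.3.2), and diarrhea is named as a class effect (2.3.1). A reader who takes the reported percent recovery as applying to everyone dosed would read it too high. If the chance of a BM changed with dose, part of any dose pattern could come from who was counted. With 6 active subjects per dose, one exclusion is enough to matter.

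**Working it through.** The plan states no recovery figure, no expected share without a BM and no sample-size calculation for this endpoint, so there is nothing to reproduce.

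**Step 1. Size of the difference, with no model.** Let k of n subjects given IW-3300 have a BM, and let S be the sum of their recoveries. The planned mean is S/k. The mean over all n, with zeros, is S/n. The ratio is n/k. For n = 6:

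| k with a BM | 6 | 5 | 4 | 3 | 2 |
|---|---|---|---|---|---|
| planned mean / all-dosed mean | 1.00 | 1.20 | 1.50 | 2.00 | 3.00 |

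Illustration with invented recoveries of 40, 30, 25, 25, 0 and 0%: the protocol rule gives 120/4 = 30%, and counting the zeros gives 120/6 = 20%.

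**Step 2. How likely exclusions are (assumption).** The documents give no probability of passing no stool in the window. Inclusion criterion 3 (Protocol 5.1.2) admits between 3 BMs per week and 3 per day. Assume a Poisson count over 24 hours with every subject at the same rate. Then q = exp(−BMs per day), the expected number excluded is 6q, P(at least one of 6 excluded) = 1 − (1 − q)^6, and the ratio of expected means is 1/(1 − q).

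| BMs per week | q | expected excluded of 6 | P(at least one) | 1/(1 − q) |
|---|---|---|---|---|
| 3 | 0.65 | 3.9 | 0.998 | 2.87 |
| 7 | 0.37 | 2.2 | 0.94 | 1.58 |
| 14 | 0.14 | 0.8 | 0.58 | 1.16 |
| 21 | 0.05 | 0.3 | 0.26 | 1.05 |

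The first and last rows put all six subjects at the limits of eligibility and are bounds, not forecasts. The window can exceed 24 hours, which lowers q. Bowel emptying is encouraged before dosing (Protocol 6.1.1), which may raise it. The enema may itself prompt a BM.

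**Step 3. Comparison across doses.** Relative to the all-dosed ratio, the high-to-low dose ratio under the protocol rule is multiplied by (1 − q_low)/(1 − q_high).

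- Equal q: 1.00, so the ratio of expected means is not distorted.
- q of 0.37 (low dose) and 0.20 (high dose): 0.63/0.80 = 0.79.
- q of 0.50 and 0.10: 0.50/0.90 = 0.56.

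These shares are hypothetical. Chance also plays a part: with q = 0.37 at both doses, two cohorts of 6 have different numbers excluded with probability 0.77.

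**Step 4. The same test on the zero-inclusive mean.** Let recovery given a BM be 30% at both doses, with q of 0.37 and 0.20. The protocol rule gives 30% and 30%. With zeros, the means are 30 × 0.63 = 18.9% and 30 × 0.80 = 24.0%. The all-dosed mean therefore also moves with the share without a BM.

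**The case against.** The strongest reply is that the protocol names no target other than drug in stool that was collected. A mean among subjects who produced stool is not biased for that group, so n/k compares two quantities and is not an error against a stated one. A zero at about 24 hours may also mean only that the drug had not yet been passed. Both points stand. The zero is recovery to Discharge, not eventual recovery, and it should be described that way. But Protocol 3.3.2 and 8.5 define the endpoint without limiting it to subjects with a BM, and the PK Analysis Set (Protocol 9.3) does not require one. The restricted mean therefore needs its label and its companion.

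A reader might go further and infer that recovery cannot be compared across doses under this rule. The documents do not support that. It needs the share without a BM to differ by dose, no such figure is given, and Protocol 2.2 reports no significant transit effect of colonic dosing in preclinical studies. Step 4 shows too that replacing one summary with the other would not by itself restore comparability. A reader might also take the near-threefold figure as the expected size, but it rests on a Poisson assumption with every subject at the eligibility minimum.

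The matter was also considered. The history of Amendment 1 (Protocol 10.7) records that the FDA asked how subjects without a stool sample would be handled, and that collection was extended to Discharge to limit missing data. Descriptive statistics include N (9.4.1), and PD data will be listed (SAP 9.1), so a careful reader could see the exclusions and approximate the all-dosed mean. The unseen PK analysis plan may add more. This lowers the stakes, but it leaves readers to rebuild a summary that the plan could provide.

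**Conclusion.** The point holds in a limited form. For amount and percent recovery to Discharge, a subject with complete collection and no BM has an observed value of 0, and Protocol 9.4.4 leaves that value out. The planned mean exceeds the all-dosed mean by n/k whenever someone has no BM and drug is recovered in the others: 1.2-fold with one of six excluded, 1.5-fold with two, and nothing if all six have a BM. This part rests only on complete collection and arithmetic.

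How many will be excluded is unknown, and distortion across doses is possible but not shown. The endpoint is exploratory and descriptive, no hypothesis is tested (Protocol 9.1), and dose escalation rests on safety and tolerability (6.6). The point is minor and worth a low-cost correction.

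**What to change.** In Protocol 9.4.4, and in the PK analysis plan to match:

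- Limit the exclusion of subjects without a BM to concentration (ng/g).
- For total amount and percent recovery to Discharge, summarize all subjects dosed with IW-3300 who had complete collection, enter 0 where there was no BM, and use arithmetic mean and median.
- Show the BM-only summary beside it, labelled as such.
- Report the number without a BM by treatment.
- State that both summaries are cut off at Discharge and that the all-dosed mean also depends on the share without a BM.

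The cost is a few sentences and one added summary, with no new data. The geometric mean and its CV%, which Protocol 9.4.1 specifies for PK data, cannot be used where zeros are present, so the all-dosed summary needs an exception to that section. The stated all-dosed recovery will be lower than the BM-only figure whenever a subject has no BM and drug is recovered in the others.
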